1. PROTOCOL SUMMARY

1.1. Synopsis

Rationale

[figure not shown]
Transthyretin Amyloid Cardiomyopathy (ATTR-CM) occurs when transthyretin amyloid fibrils infiltrate the myocardium, leading to deposits of extracellular amyloid. Deposition of transthyretin fibrils occurs between the myocardial cells and produces a thickening and stiffening of the myocardial tissue. This infiltration of the myocardium results in diastolic dysfunction progressing to restrictive cardiomyopathy, congestive heart failure, and ultimately death.

The most frequent form of heart failure (HF) in patients with ATTR-CM is HF with preserved ejection fraction (HFpEF). HFpEF is also the most common form of heart failure in elderly patients and accounts for up to 50% of HF-related hospital admissions. It has recently been described that ATTR-CM is significantly underdiagnosed and may be more common than current prevalence estimates. The purpose of this study is to assess the prevalence of ATTR-CM in the HFpEF population.

Objectives and Endpoints

Primary Objective(s):	Primary Endpoint(s):
To assess the prevalence of ATTR-CM among patients with HFpEF within a clinically at-risk population.	Estimate of global prevalence of ATTR-CM in HFpEF patients. Diagnosis of ATTR-CM is defined by: 
• Cardiac Scintigraphy Grade 1, with confirmation of ATTR by cardiac biopsy, or:• Cardiac Scintigraphy Grade 2 or above.
Secondary Objective(s):	Secondary Endpoint(s):
To assess variations in prevalence of ATTR-CM (wild-type [WT] and hereditary) among patients with HFpEF at a country, regional, and global level.	
• Estimate of prevalence of ATTR-CM in patients with HFpEF based on:
• Geographical or regional distribution;• Age categories;• Gender.• Proportion of patients with WT and hereditary forms among patients diagnosed with ATTR-CM.• Baseline characteristics of HFpEF patients

	
with and without ATTR-CM:
 
• New York Heart Association (NYHA) classification;• NT-proBNP.
--	---

CCI

CCI

Overall Design

This study is a global, multi-center epidemiology study designed to estimate the global prevalence of ATTR-CM in participants with HFpEF within a clinically at-risk population.

Number of Participants

The empirical estimate for the prevalence of ATTR-CM in HFpEF participants is approximately 10%. The study will enroll approximately 2000 HFpEF participants within whom it is expected to detect 200 ATTR-CM participants. Enrollment will be stopped if 200 ATTR-CM participants are identified before 2000 HFpEF are enrolled. No formal sample size calculation was performed. A sample size of 2000 HFpEF participants would be sufficient to inform treatment guidelines and yield an estimate for the global prevalence of ATTR-CM in HFpEF participants with a precision of $\pm 2.5\%$.

Statistical Methods

The primary endpoint is an estimate of the global prevalence of ATTR-CM in HFpEF participants. Diagnosis of ATTR-CM is defined as:

- Cardiac Scintigraphy Grade 1, with confirmation of ATTR by cardiac biopsy; or
- Cardiac Scintigraphy Grade 2 or above.

This global prevalence estimate will be obtained by dividing the number of participants who are diagnosed with ATTR-CM in the study by the total number of HFpEF participants evaluated. A 95% confidence interval on the estimate will also be calculated.

As secondary analysis, prevalence will be estimated for:

- Regions and countries;
- Age categories (60-64, 65-69, 70-74, 75-79, 80-85, >85);

- Gender (male, female).

Prevalence estimates along with 95% confidence interval (CI) will be generated for regions and countries with at least 50 participants. For regions and countries that enroll fewer than 50 participants, prevalence will not be estimated. Regions will be defined in the statistical analysis plan. The proportion of HFpEF participants who were diagnosed with wild-type and variant ATTR-CM will be descriptively summarized.

As a general rule, the secondary endpoints other than the prevalence estimates and all CCI [REDACTED] reported as numerical values will be analyzed descriptively using mean, standard deviation, median, minimum, and maximum. Endpoints that are categorical will be summarized using frequency tables.

Analysis by Scintigraphy:

Participants who are diagnosed with ATTR-CM will be analyzed by scintigraphy grades (Grade 1, 2, or 3) using the 6-MWT, NT-proBNP, medical history, demographics (including age, TTR Genotype, gender and race), NYHA classification (Class I, II, III, or IV), and all CCI [REDACTED]

Analysis by Disease Status:

Participants who are diagnosed with ATTR-CM will be analyzed by NYHA Classification (Class I, II, III, or IV) using the 6-MWT, NT-proBNP, medical history, demographics (including age, TTR Genotype, gender, and race) CCI [REDACTED]

Participants who are diagnosed with ATTR-CM will also be analyzed by 6-MWT quartile groups using NYHA classification (Class I, II, III, or IV), NT-proBNP, medical history, demographics (including age, TTR Genotype, gender, and race) CCI [REDACTED]

Analysis Comparing ATTR-CM participants with HFpEF patients without ATTR-CM:

HFpEF participants diagnosed with ATTR-CM will be compared with HFpEF participants not diagnosed with ATTR-CM descriptively using medical history, demographics (including age, TTR Genotype, gender, and race) CCI [REDACTED]

Medical history data will be used to generate descriptive statistics for time from symptom onset to HFpEF diagnosis and time from symptom onset to ATTR-CM diagnosis.

Endpoints measuring proportion of participants (NYHA Classification and symptoms of interest from medical history) will be compared between HFpEF participants diagnosed with ATTR-CM and those that are not diagnosed with ATTR-CM. The Chi-square test will be used to compare the proportions between these 2 groups of HFpEF participants. Fisher's exact test will be used instead of the chi-square test if any one of the cells has ≤ 5 participants. Secondary CCI [REDACTED] numerical endpoints that are normally distributed will be

compared between 2 groups of HFpEF participants using a t-test. Endpoints that are not normally distributed will be compared using the Wilcoxon rank sum test.

Safety Analysis:

Adverse events (AEs) and research related injuries (RRI) collected at Visit 1 or during follow-up, will be summarized overall and separately for HFpEF participants diagnosed with ATTR-CM and HFpEF participants not diagnosed with ATTR-CM.

1.2. Rationale

Transthyretin Amyloid Cardiomyopathy (ATTR-CM) occurs when transthyretin amyloid fibrils infiltrate the myocardium, leading to deposits of extracellular amyloid. Deposition of transthyretin fibrils occurs between the myocardial cells and produces a thickening and stiffening of the myocardial tissue. This infiltration of the myocardium results in diastolic dysfunction progressing to restrictive cardiomyopathy, congestive heart failure, and ultimately death.

The most frequent form of HF in patients with ATTR-CM is HF with preserved left ventricular ejection fraction (HFpEF).¹ HFpEF is also the most common form of HF in elderly patients and accounts for up to 50% of HF-related hospital admissions.^{2,3} It has recently been described that ATTR-CM is significantly underdiagnosed and may be more common than current prevalence estimates. The purpose of this study is to assess the prevalence of ATTR-CM in the HFpEF population.

1.3. Schema

Not Applicable.

1.4. Schedule of Activities (SoA)

The SoA table provides an overview of the protocol visits and procedures. Refer to the [Section 8](#) of the protocol for detailed information on each procedure and assessment required for compliance with the protocol.

The investigator may schedule visits (unplanned visits) in addition to those listed in the SoA table, in order to conduct evaluations or assessments required to protect the well-being of the participant.

Visit Identifier	Screening ^b	Visit 1 ^b	Follow-up 1 ^{bc}	Follow-up 2 ^{bf}
Visit Day		Day 1	14 Days Post Last Study Visit	6 Months Post Last Study Visit
Visit Window	Days -28 to -3		+10 Days	±30 Days
Informed consent	X			
Review entrance criteria	X			
Echocardiography ^a	X			
Medical History	X			
Record current medications		X		X
Demography	X			
NYHA classification		X		
Physical Examination including height and body weight	X			
Vital Signs	X			
CCI				
Scintigraphy		X		
TTR genotyping ^c		X		
CCI				
Laboratory samples				
Cardiac Biomarkers (NT-proBNP)		X		
Serum/Urine tests for primary (light chain) amyloidosis ^c		X		
Blood and Urine specimens for ATTR-CM biomarkers		X		
CCI				
Inform participant of diagnosis			X	
Adverse Event reporting	X	X	X	
Vital Status				X
Subsequent diagnosis testing				X

Abbreviations: NYHA = New York Heart Association; CCI
 CCI TTR – transthyretin; CCI
 CCI nal

- a. Echo performed if previous echo was ≥6 months prior to screening visit. If echo was performed within 6 months prior to screening and results are available, the echo can be used for study and does not need to be repeated.
- b. May be performed by remote participant visit.
- c. Participants should be followed for 14 days after the last study visit day to collect any AE/RRi information.
- d. Or at early discontinuation.

- e. Sample collected from all participants, only those samples from participants that are scintigraphy Grade 1, 2, or 3 will be analyzed.
- f. For participants with scintigraphy grade 1, 2 or 3.

2. STUDY INTRODUCTION

2.1. Rationale

Transthyretin Amyloid Cardiomyopathy (ATTR-CM) occurs when transthyretin amyloid fibrils infiltrate the myocardium, leading to deposits of extracellular amyloid. Deposition of transthyretin fibrils occurs between the myocardial cells and produces a thickening and stiffening of the myocardial tissue. This infiltration of the myocardium results in diastolic dysfunction progressing to restrictive cardiomyopathy, congestive heart failure, and ultimately death.

The most frequent form of HF in patients with ATTR-CM is HF with preserved left ventricular ejection fraction (HFpEF).⁴ HFpEF is also the most common form of HF in elderly patients and accounts for up to 50% of HF-related hospital admissions.^{5,6} It has recently been described that ATTR-CM is significantly underdiagnosed and may be more common than current prevalence estimates. The purpose of this study is to assess the prevalence of ATTR-CM in the HFpEF population.

2.2. Background

Transthyretin (TTR) amyloidosis is a rare protein misfolding disease with a broad spectrum of manifestations. The condition is caused by the destabilization and dissociation of the native TTR tetramer which can result in misfolding and the formation of amyloid fibrils and progressive amyloid deposition in tissues.^{7,8,9,10} This can occur in amounts sufficient to impair normal functioning. The 2 major phenotypes which form the spectrum of ATTR amyloidosis are transthyretin amyloid polyneuropathy (ATTR-PN), which primarily affects the peripheral and autonomic nerves, and ATTR-CM which primarily affects the myocardium. These clinical manifestations may occur in isolation or together. Both result in progressively impaired function, and ultimately in death.

ATTR-CM is a fatal disorder, characterized by the deposition of misfolded transthyretin amyloid fibrils in the ventricular walls (extra-myocardial), causing progressive disruption in the ability of the heart to effectively pump blood through the circulatory system. In ATTR-CM, the myocardium is the key site of ATTR deposition, and accumulation can lead to diastolic dysfunction progressing to restrictive cardiomyopathy and heart failure.

ATTR-CM can be inherited as an autosomal dominant trait caused by mutation in the TTR gene, or by deposition of wild-type transthyretin protein, previously called senile systemic or senile cardiac amyloidosis.^{10,11} The median age of patients with wild-type ATTR-CM has been reported as 75 years of age at diagnosis.¹² In the Tafamidis for ATTR-CM Trial (ATTR-ACT) the average age of patients was 74.5 ± 7.2 (standard deviation).¹³ The hereditary (genetic variants) form of disease can affect multiple generations in a family and have a substantial emotional impact on patients and their families.¹⁴ ATTR-CM is associated with genetic variants of TTR such as Val122Ile and Leu111Met (also known as familial amyloid cardiomyopathy) but may also occur in the absence of a specific mutation (i.e., wild-type TTR).^{10,11} The Val122Ile mutation allele occurs in 3.3% to 4.0% of the US African-American population,^{15,16} and is exceedingly rare in White patients. Median survival from diagnosis for patients with ATTR-CM has been reported as 41 months for patients with

a Val122Ile mutation and 46 months for patients with ATTR-CM due to wild-type TTR,¹⁷ with most patients dying from cardiac causes, including sudden death, CHF, and myocardial infarction.^{18,19} Untreated ATTR-CM is currently associated with mean progression to death within 24 to 36 months (median survival 25.6 months) of diagnosis for variants and up to 60 months (median survival 43.0 months) for wild type.²⁰

The prevalence of ATTR-CM is defined as rare, but no prevalence estimates have been published. There are more than 120 mutations in the TTR gene which cause a variable phenotype determined by the relative extent of amyloid deposition in the myocardium and peripheral nerves.²¹ Though prevalence of wild-type TTR is uncertain, studies using a non-biopsy approach to diagnosis^{22,23} report a prevalence of 13% in HF patients with preserved ejection fraction,²⁴ 16% in patients undergoing transcatheter aortic valve replacement for severe aortic stenosis,²⁵ and 5% of patients with presumed hypertrophic cardiomyopathy.²⁶

ATTR-CM (due to wild-type or variant TTR) uniformly presents with the typical symptoms of HF (restrictive cardiac disease) including shortness of breath, dyspnea on exertion, orthostatic hypotension, syncope, and dysrhythmias including atrial fibrillation. Signs of ATTR-CM are evaluated via testing performed as part of routine HF assessment including electrocardiography, echocardiography, and cardiac biomarkers (e.g., N-terminal prohormone B type natriuretic peptide [NT-proBNP]). As the symptoms are very non-specific, a diagnosis of ATTR-CM may often be delayed for years.^{27,28} An electrocardiogram (ECG) and echocardiogram aid in the diagnosis. Definitive confirmation of ATTR-CM has been typically achieved through a cardiac biopsy,²⁹ although cardiac magnetic resonance imaging (MRI) and scintigraphy are increasingly used to confirm evidence of disease. A non-biopsy approach using technetium-labeled bone scintigraphy tracers has been validated as a method for identification of patients with ATTR-CM. This approach is highly sensitive and specific for diagnosing ATTR-CM due to both hereditary and wild-type disease,^{18,19,28} and can detect ATTR prior to an increase in left ventricular wall thickness or the development of the clinical syndrome of heart failure and a rise in cardiac biomarkers^{30,31} and even predict prognosis.^{21,30} Early identification and treatment is now more likely with the availability of effective diagnostic tools and therapy.

The most frequent form of HF in patients with ATTR-CM is HF with preserved left ventricular ejection fraction (HFpEF). HFpEF is also the most common form of HF in elderly patients and accounts for 50% of HF-related hospital admissions. It has recently been described that ATTR amyloidosis is significantly underdiagnosed, taking into consideration that both the clinical presentation and the symptoms are non-specific. The aim of this epidemiology study is to assess the prevalence of ATTR-CM in a clinically at risk HFpEF population.

2.3. Benefit/Risk Assessment

Participants in this study will already be diagnosed with HFpEF. Through participation in this study a further diagnosis of ATTR-CM will be assessed which will allow the health care provider to consider further treatment options for the participant. Potential risk includes those inherent from the procedures described.

3. OBJECTIVES AND ENDPOINTS

Primary Objective(s):	Primary Endpoint(s):
To assess the prevalence of ATTR-CM among patients with HFpEF within a clinically at-risk population.	Estimate of global prevalence of ATTR-CM in HFpEF patients. Diagnosis of ATTR-CM is defined as: 
• Cardiac Scintigraphy Grade 1, with confirmation of ATTR by cardiac biopsy, or:• Cardiac Scintigraphy Grade 2 or above.
Secondary Objective(s):	Secondary Endpoint(s):
To assess variations in prevalence of ATTR-CM (wild-type [WT] and hereditary) among patients with HFpEF at a country, regional, and global level.	
• Estimate of prevalence of ATTR-CM in patients with HFpEF based on:
• Geographical or regional distribution;• Age categories;• Gender.• Proportion of patients with WT and hereditary forms among patients diagnosed with ATTR-CM.• Baseline characteristics of HFpEF patients with and without ATTR-CM:
• New York Heart Association (NYHA) classification;• NT-proBNP.

CCI

CCI

4. STUDY DESIGN

4.1. Overall Design

This study is a global, multi-center epidemiology study designed to estimate the global prevalence of ATTR-CM in participants with HFpEF within a clinically at-risk population. The study will enroll approximately 2000 patients.

4.2. Scientific Rationale for Study Design

It has recently been described that ATTR amyloidosis is significantly underdiagnosed, taking into consideration that both the clinical presentation and the symptoms are non-specific. The most frequent form of HF in patients with ATTR-CM is HF with preserved left ventricular ejection fraction (HFpEF). The aim of this epidemiology study is to assess the prevalence of ATTR-CM in a clinically at risk HFpEF population. Inclusion of an age criteria of ≥ 60 years enables only at-risk HFpEF participants to be enrolled.

Definitive diagnosis of ATTR-CM may include invasive tissue biopsy. Extracardiac biopsy has a low diagnosis yield in ATTR amyloidosis, particularly in wild-type ATTR (ATTRwt). Therefore, in the setting of high clinical suspicion and a negative extracardiac biopsy, endomyocardial biopsy would be required. This invasive diagnostic approach carries

associated complications and delays in diagnosis.²² Alternatively, noninvasive cardiac scintigraphy has marked a crucial change in the diagnostic workup of the disease. Data show that a Grade 2 or 3 uptake, in the absence of monoclonal proteins on serum and urine immunofixation electrophoresis and serum free light chain assay, is associated with 100% sensitivity and 100% specificity for cardiac ATTR amyloidosis.²² In the case of Grade 1 uptake, histological confirmation through endomyocardial biopsy with typing of amyloid is required.

4.3. Justification for Dose

Not applicable.

4.4. End of Study Definition

The end of study is when all participants have completed all applicable study visits (including Follow-up Visit 2,) as shown in the SoA.

5. STUDY POPULATION

This study can fulfill its objectives only if appropriate participants are enrolled. The following eligibility criteria are designed to select participants for whom participation in the study is considered appropriate. All relevant medical and nonmedical conditions should be taken into consideration when deciding whether a particular participant is suitable for this protocol.

Prospective approval of protocol deviations to recruitment and enrollment criteria, also known as protocol waivers or exemptions, is not permitted.

5.1. Inclusion Criteria

Participants are eligible to be included in the study only if all of the following criteria apply:

1. Male and female participants ≥ 60 years of age at time of screening.
2. Medical history of heart failure (HF) with:
 - a. At least 1 episode with clinical evidence of HF (without hospitalization) by signs or symptoms of volume overload or elevated intracardiac pressures that required/requires treatment with a diuretic for improvement; OR
 - b. 1 prior hospitalization for HF.
3. Left ventricular ejection fraction (LVEF) $> 40\%$.
4. End-diastolic interventricular septal wall thickness (IVST) ≥ 12 mm.
5. Willing and able to undergo scintigraphy.

6. Capable of giving signed informed consent as described in [Section 10.1.2](#) which includes compliance with the requirements and restrictions listed in the informed consent document (ICD) and in this protocol.
7. Participants who are willing and able to comply with all scheduled visits, laboratory tests, and other study procedures.

5.2. Exclusion Criteria

Participants are excluded from the study if any of the following criteria apply:

1. Diagnosis of heart failure with reduced ejection fraction (HFrEF) ($EF \leq 40\%$).
2. Prior clinical history of myocardial infarction, CABG or multi-vessel obstructive coronary disease ($>50\%$ stenosis of ≥ 2 epicardial coronary arteries).
3. Presence or history of any severe valvular heart disease (obstructive or regurgitant).
4. A confirmed diagnosis of a non-amyloid infiltrative cardiomyopathy (i.e., cardiac sarcoidosis, hemochromatosis), muscular dystrophies, cardiomyopathy with reversible causes, hypertrophic obstructive cardiomyopathy with known genetic etiology, or known pericardial constriction.
5. Any type of diagnosed amyloidosis (e.g., amyloid A amyloidosis, primary [light chain] amyloidosis) or prior diagnosis of ATTR-CM.
6. Investigator site staff or Pfizer employees directly involved in the conduct of the study, site staff otherwise supervised by the investigator, and their respective family members.
7. Other medical or psychiatric condition including recent (within the past year) or active suicidal ideation/behavior or laboratory abnormality that may increase the risk of study participation or, in the investigator's judgment, make the participant inappropriate for the study.

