5.5. Screen Failures

Screen failures are defined as participants who consent to participate in the clinical study but are not subsequently entered in the study. A minimal set of screen failure information is required to ensure transparent reporting of screen failure participants to meet the Consolidated Standards of Reporting Trials (CONSORT) publishing requirements and to

respond to queries from regulatory authorities. Minimal information includes screen failure details such as demography, eligibility criteria, and any SAE. Individuals who do not meet the criteria for participation in this study (screen failure) will be recorded as a screen failure but may be rescreened at a later date. Rescreened participants will be assigned a new screening number. Pfizer approval must be provided prior to re-screening a participant.

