9. STATISTICAL CONSIDERATIONS

Detailed methodology for summary and statistical analyses of the data collected in this study will be documented and will be maintained by the sponsor.

The primary completion date (PCD) for the global prevalence estimate will be the date when all enrolled participants have either been diagnosed with ATTR-CM (scintigraphy grades 2 or 3), have scintigraphy grade 1 or found to be negative for ATTR-CM (scintigraphy grade 0) and have completed Follow-up Visit 1. Results will be reported after PCD and at the end of study (LPLV for participants with scintigraphy grade 1, 2 or 3).

The empirical estimate for the prevalence of ATTR-CM in HFpEF participants is approximately 10%. The study will enroll approximately 2000 HFpEF participants within whom it is expected to detect 200 ATTR-CM participants. Enrollment will be stopped if 200 ATTR-CM participants are identified before 2000 HFpEF are enrolled. No formal sample size calculation was performed. A sample size of 2000 HFpEF participants would be sufficient to inform treatment guidelines and yield an estimate for the global prevalence of ATTR-CM in HFpEF participants with a precision of $\pm 2.5\%$.

The primary endpoint is an estimate of the global prevalence of ATTR-CM in HFpEF participants. Diagnosis of ATTR-CM is defined as:

- Cardiac Scintigraphy Grade 1, with confirmation of ATTR by cardiac biopsy; or
- Cardiac Scintigraphy Grade 2 or above.

This global prevalence estimate will be obtained by dividing the number of participants who are diagnosed with ATTR-CM in the study by the total number of HFpEF participants evaluated. A 95% confidence interval on the estimate will also be calculated.

As secondary analysis, prevalence will be estimated for:

- Regions and countries.
- Age categories (60-64, 65-69, 70-74, 75-79, 80-85, >85).
- Gender (male, female).

Prevalence estimates along with 95% CI will be generated for regions and countries with at least 50 participants. For regions and countries that enroll fewer than 50 participants, prevalence will not be estimated. Regions will be defined in the statistical analysis plan. The proportion of HFpEF participants who were diagnosed with wild-type and variant ATTR-CM will be descriptively summarized.

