3.2. Secondary Endpoint(s)

The secondary endpoints are listed below will consider a participant as diagnosed with ATTR-CM based on the definition in [Section 6.1.1.1](#).

- Estimate of prevalence of ATTR-CM in participants with HFpEF within the following subgroups, where prevalence within each subgroup is defined as the number of participants meeting the diagnosis criteria in [Section 6.1.1.1](#) divided by the number of evaluable participants in the study in the given subgroup category:
 - Regions (North America, Europe, Asia);
 - Age categories (60-64, 65-69, 70-74, 75-79, 80-85, >85);
 - Gender (male, female).
- Participants diagnosed with ATTR-CM will be evaluated for TTR genotype, ie, wild-type or hereditary form. The proportions of these two genotypes will be evaluated as a secondary endpoint
- Baseline characteristics of HFpEF participants with and without ATTR-CM:
 - NYHA classification: Participants will be evaluated using the New York Heart Association classification at baseline visit (day 1). Detailed description of each class (Class I, Class II, Class III, Class IV) is available in Section 8.2.12 of the protocol.
 - NT-proBNP: A biomarker that will be assessed during visit 1.

CCI

CCI

CCI

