4. ANALYSIS SETS (POPULATIONS FOR ANALYSIS)

All primary, sensitivity, and secondary endpoints estimating prevalence will be based on “Evaluable Analysis Set” defined below. All other endpoints, including CCI and safety endpoints will be evaluated using “All Enrolled Analysis Set”.

Population	Description
All Enrolled Analysis Set	All participants who meet the inclusion/exclusion criteria and completed Visit 1
Evaluable Analysis Set	All participants who meet the inclusion/exclusion criteria and completed Visit 1, excluding participants with Cardiac Scintigraphy assessed as non-evaluable

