6. ANALYSES AND SUMMARIES

6.1. Primary Endpoint(s)

The primary endpoint is an estimate of the global prevalence of ATTR-CM in HFpEF participants. Diagnosis of ATTR-CM is defined as:

- Cardiac Scintigraphy Grade 1, with confirmation of ATTR by cardiac biopsy during the study period, or:
- Cardiac Scintigraphy Grade 2 or above.

The primary endpoint will be evaluated by dividing the number of participants who are classified as ATTR-CM positive by Cardiac Scintigraphy (as noted above) by the total number of HFpEF evaluable participants in the study. The proportion of Scintigraphy Grade 1 participants that are diagnosed with ATTR-CM will be estimated. Scintigraphy

Grade 1 participants that are diagnosed with ATTR-CM using a criteria other than cardiac biopsy and participants lost to follow-up without a confirmation of cardiac biopsy will be assumed as not diagnosed with ATTR-CM in the primary analysis. Exact 95% confidence intervals for the prevalence will be calculated using the method of Clopper and Pearson.¹ The primary analysis will be generated using the “Evaluable Analysis Set”.

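### The trial excludes patients already diagnosed with ATTR-CM, so it estimates the prevalence of previously undiagnosed disease, not the global prevalence of ATTR-CM that the endpoint names.

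*Protocol*

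**What the plan says.** Exclusion 5 in Protocol 5.2 reads "Any type of diagnosed amyloidosis (e.g., amyloid A amyloidosis, primary [light chain] amyloidosis) or prior diagnosis of ATTR-CM". The opening of Protocol 5 rules out waivers of the entry criteria.

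Protocol 9 obtains the primary estimate by "dividing the number of participants who are diagnosed with ATTR-CM in the study by the total number of HFpEF participants evaluated". SAP 4 defines the Evaluable Analysis Set as "All participants who meet the inclusion/exclusion criteria and completed Visit 1, excluding participants with Cardiac Scintigraphy assessed as non-evaluable", and uses it for the primary, sensitivity and subgroup prevalence estimates.

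The primary objective (Protocol 3) is "To assess the prevalence of ATTR-CM among patients with HFpEF within a clinically at-risk population". SAP 6.1 states: "The primary endpoint is an estimate of the global prevalence of ATTR-CM in HFpEF participants". SAP 3.2 carries the same label into its secondary endpoints: "Estimate of prevalence of ATTR-CM in participants with HFpEF within the following subgroups", the subgroups being region, age and gender.

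The one limiting phrase, clinically at-risk, is explained only in Protocol 4.2: "Inclusion of an age criteria of ≥ 60 years enables only at-risk HFpEF participants to be enrolled".

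**The concern.** The name of the endpoint and the quantity computed do not match. Prevalence of a disease counts everyone who has it, whether or not it is already known. This design removes the known cases before counting, so it measures how much undiagnosed ATTR-CM is found when eligible patients are scanned. That is a useful quantity, but a different one.

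Protocol 9 expects the result to feed into treatment guidelines. A headline prevalence is usually quoted without the exclusion list, so readers would take the case-finding yield for the total burden.

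The secondary objective, variation by country and region, is exposed as well. If prior diagnosis is more complete in one region than in another, the exclusion alone can create or hide a regional difference.

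**Working it through.** **Step 1. Who can be counted.** A patient with known ATTR-CM fails exclusion 5, cannot be waived in, is not in the Evaluable Analysis Set, and so contributes to neither numerator nor denominator. This holds for the primary, sensitivity and subgroup prevalence estimates alike.

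**Step 2. The plan's own figures.** Protocol 9 assumes about 10% prevalence and 2000 participants: 2000 × 0.10 = 200 expected cases, as stated. The Clopper-Pearson 95% interval at 200/2000 is 8.72% to 11.40%, a half-width of (11.40 − 8.72)/2 = 1.34 points. The Wald half-width is 1.96 × √(0.10 × 0.90/2000) = 1.31 points. The stated ±2.5% is therefore met only as an upper bound.

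**Step 3. Effect of the exclusion alone.** Let p be the all-case prevalence in the otherwise eligible population and d the share of those cases already diagnosed. Removing the known cases leaves p(1 − d) cases among 1 − pd patients, so the trial estimates

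q = p(1 − d)/(1 − pd), with shortfall p − q = p(1 − p)d/(1 − pd).

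The documents do not give d, so the values below are assumptions. They also do not say whether their 10% counts known cases; p = 10% is taken here as all-case.

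| d | q | shortfall (points) |
|---|---|---|
| 5% | 0.095/0.995 = 9.5% | 0.45 |
| 10% | 0.090/0.990 = 9.1% | 0.9 |
| 20% | 0.080/0.980 = 8.2% | 1.8 |
| 30% | 0.070/0.970 = 7.2% | 2.8 |
| 50% | 0.050/0.950 = 5.3% | 4.7 |

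**Step 4. When this exceeds sampling error.** Setting the shortfall equal to h at p = 0.10 gives d = h/(0.09 + 0.1h).

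- h = 1.31 to 1.34 points: d is about 14% to 15%.
- h = 2.5 points: d = 0.025/0.0925 = 27%.

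With 2000 evaluable participants the expected 95% interval is about 7.9% to 10.5% at d = 10%, which still covers 10%. At d = 20% it is about 7.0% to 9.4%, which does not.

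**Step 5. Regional contrast.** Take two regions with the same all-case prevalence of 10%, one with d = 5% and the other with d = 30% (both assumed). The trial would estimate 9.5% and 7.2%, an apparent difference of 2.3 points with no true difference behind it.

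**The case against.** The strongest reply is that nothing is hidden. The exclusion is stated, the SAP defines its denominator as evaluable participants, and the Protocol 9 estimator refers to diagnosis during the study. The rationale sections stress underdiagnosis, so a careful reader can see that this is case-finding. That supports keeping the exclusion, but it does not repair the label. Protocol 1.2 gives the purpose as assessing prevalence in the HFpEF population, and the endpoint sentences carry no restriction to undiagnosed disease.

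A second reply is that a patient with known ATTR-CM is not at risk of it, so the at-risk wording already covers the point. No visible text defines the phrase that way. Protocol 4.2 links it to age, and the endpoint sentences in Protocol 9 and SAP 6.1 omit it.

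Three points stand.

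- **Size is undetermined.** The only evidence on d in the documents is the statement that the disease is underdiagnosed, which points to a low value. At d = 5% or 10% the shortfall is within the sampling half-width.
- **Net direction for all HFpEF is not established.** Requiring septal thickness of at least 12 mm, or counting Grade 2 or above with no light-chain condition, may raise the estimate. Exclusion 5 also removes other diagnosed amyloidosis from the denominator, a small upward effect: removing 1% of it would turn 10% into 0.10/0.99 = 10.1%.
- **The regional effect is a possibility.** The documents give no regional rates of prior diagnosis.

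Parts of SAP 2.2 and 3.1 are not in the available text, so a qualifier there cannot be ruled out. Protocol 3, 4.1, 4.2 and 9 contain none.

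**Conclusion.** The concern holds. Followed exactly, the plan would report under the name of global ATTR-CM prevalence a quantity that leaves out all previously diagnosed cases. This follows from the eligibility rule and the analysis-set definition and needs no numerical assumption.

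Taken alone, the exclusion lowers the estimate whenever d is above zero. On an assumed all-case prevalence of 10%, the shortfall runs from 0.45 points (d = 5%) to 4.7 points (d = 50%). It may be small in practice, but no planned analysis would show its size. The mismatch should be corrected. It is a fault of labelling and interpretation and does not invalidate the design.

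**What to change.** Keep the exclusion and change the claim. In Protocol 1.1, 3, 4.1 and 9, and SAP 2.1, 3.2, 6.1 and 6.2, reword the objective and the primary and secondary prevalence endpoints as the prevalence of previously undiagnosed ATTR-CM in patients with HFpEF who meet the entry criteria. Word the conclusion the same way. Add a sentence that regional differences may partly reflect different rates of prior diagnosis.

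At most, report descriptively how many screen failures were due to prior ATTR-CM. Do not use that count to correct the prevalence. Protocol 5.5 says "Screen failures are defined as participants who consent to participate in the clinical study but are not subsequently entered in the study", so known cases who were never approached or did not consent are missing from it.

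The cost is wording: no new data, participants or analyses. SAP 2 says that major changes to the primary endpoint definition will also appear in a protocol amendment, so one may be needed, with the ethics review that Protocol 10.1.1 requires. The sponsor also accepts a narrower claim.
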